5.2.2 Preparatory Sessions and Baseline Measures

Subjects who do not complete all screening activities will not be enrolled. Eligibility may be discussed by phone after screening is complete and at the time Visit 3 is scheduled but the final confirmation will occur at Visit 3. If all inclusion criteria and no exclusion criteria are met, eligibility will be confirmed with the subject.

- Complete a final review of inclusion/exclusion criteria.
- Assess general wellbeing.
- Confirm eligibility and willingness to participate in study.
- Enroll subject and issue subject number.
- Ensure medical history and medication history is complete. After enrollment new events will be collected as AEs and new medications, as described in Section 8.5 and Section 9.0.
- Assess status of symptoms at baseline specific to the study population.
- Discuss medication tapering, if applicable. Upon confirmation of eligibility, the PI will consult the prescribing physician to initiate medication tapering for

subjects who must refrain from taking a psychiatric medication for the study. Tapering will follow a time course appropriate for the medication given its half-life, with the first experimental session scheduled to occur after complete washout.

The subjects will undergo three preparatory sessions lasting approximately sixty minutes each with their therapist team, prior to their first experimental session. The first preparatory session will take place at Visit 1 after enrollment confirmation. Baseline measures will be spread out among preparatory sessions in order to reduce participant fatigue from completion of measures.

The therapists will work with the subject to prepare for MDMA-assisted therapy. The therapists and subject will seek to form a strong working relationship with each other as the therapists help the subject prepare for upcoming experimental sessions. Preparatory sessions will promote a safe set and setting for confronting emotions and are intended to develop therapeutic alliance.

During preparatory sessions:

- a. Therapists may record all sessions to audio and video. Subjects may access video recordings from these sessions upon request via a secure and password protected website.
- b. Collect AEs and medications, as described in Section 8.5 and Section 9.0.
- c. Assess status of symptoms at baseline specific to the study population.
- d. The therapists will inquire about any possible changes in the subject's health to ensure that subject continues to meet eligibility criteria and, if applicable, will confirm that the subject has appropriately tapered off of medications.
- e. The subject and therapists will discuss goals for the experimental session and will review what will happen during the experimental session.
- f. During one of the preparatory sessions, the therapists will introduce the subject to the staff at the outpatient research center who they will be most likely to encounter before, during, or after treatment sessions.
- g. The Support Partner will meet with the therapists prior to the first experimental session to review and confirm their role and responsibilities and sign an ICF addendum. There must be mutual agreement between the subject and therapists concerning the presence of the Support Partner.
- h. The therapists will administer the C-SSRS just prior to beginning the second preparatory session, unless a subject is still undergoing medication washout. Subjects still undergoing medication washout will complete the C-SSRS during the second preparatory session or at a point after washout is complete prior to the first experimental session.
- i. Assess general wellbeing at each preparatory session.
- j. At the end of the first preparatory session, subjects will complete:
 - a. BDI-II
 - b. STAI
 - c. PSS
 - d. IRI

- e. RSES
- k. At the end of the second preparatory session, subjects will complete the TASIT.
- l. The second preparatory session will include a comprehensive tour of the treatment location and introductions to all available research and support personnel who subjects are likely to see during experimental sessions.
- m. At the end of the third preparatory session, subjects will complete:
 - a. ERQ
 - b. TAS-20
 - c. QoL-Q
- n. During the third and last preparatory session, give the Reminder of Study Rules to the subject, which includes instructions and restrictions for conduct prior to receiving the drug. Subjects must agree to:
 - Refrain from eating after 24:00 (midnight) the evening before the experimental session.
 - Ingest only alcohol-free liquids after 24:00 (midnight) the evening before the experimental session.
 - Refrain from the use of any psychoactive drug, with the exception of caffeine or nicotine, within 24 hours of each experimental session.
 - Not use caffeine or nicotine for two hours before and six hours after ingesting the drug, or until therapists deem it safe to do so.

5.2.3 Experimental sessions

Subjects will receive two blinded experimental sessions of therapy assisted by MDMA or placebo, scheduled one month apart after integrative sessions are complete. Procedures for drug-assisted therapy will remain the same across all sessions. During experimental sessions, there will be periods of structured and unstructured interactions. The structured interactions will be selected based on elements of therapeutic interventions that are currently in use in this population for the treatment of social anxiety. Structured interactions during experimental sessions are intended to develop the therapeutic relationship between subjects and therapists and to enhance skills of social perception through administration of the TASIT. The unstructured interactions will include an array of therapeutic activities and approaches that would be appropriate for subjects to engage in during experimental sessions. All subjects will follow the same schedule of structured alternating with unstructured periods but will be able to choose from a selection of activities during each unstructured period. Examples include, but are not limited to, working with art supplies, listening to preselected music, writing in journals, silent introspection, and engaging in rapport-building interactions with therapists. The therapists will create and communicate a setting of safety and support the subject during periods of inner focus. Therapists will use a largely nondirective approach. Therapists will provide encouragement for staying present with difficult experiences. Therapists may occasionally offer gentle guidance or redirection as a choice to encourage collaborative exploration if the subject repeatedly avoids interpersonal contact. Therapists will use music to support the experience without being intrusive.

Table 4. Schedule of Procedures for Experimental Sessions

Approximate Time	Procedure or Action
------------------	---------------------

9:00	Urine drug screen and pregnancy test. Subject acclimated to environment, C-SSRS
9:45	Baseline Blood Pressure (BP), Pulse, SUD
10:00	MDMA Administration , begin recording to audio and video
11:00	BP, Pulse, SUD, BT
12:00	BP, Pulse, BT, SUD, During 2 nd exp. session only: Blood draw
12:15	Start TASIT (EET, SM-I, SM-E)
13:00	BP, Pulse, BT, SUD
14:00	BP, Pulse, BT, SUD
15:00	BP, Pulse, BT, SUD
16:00	BP, Pulse, BT, SUD, C-SSRS, General Wellbeing
17:00	BP, Pulse, BT, SUD, End of session

Pre-drug:

- a. At least 24 hours prior to the first experimental session the subject will be randomized. The PI will obtain the container assignment using a web-based randomization program prior to the blinded sessions.
- b. On the day of the experimental session, the subject will arrive approximately one to one and a half hours prior to drug administration.
- c. Confirm continuing eligibility by reviewing inclusion/exclusion criteria.
- d. Collect information on phase of menstrual cycle for female subjects.
- e. Perform a urine drug screen. A positive drug screen will be reviewed by the PI and may be cause for delaying drug administration to a later time, rescheduling the session to a later date, or withdrawing the subject from the study.
- f. If a woman is of childbearing potential, perform a urine pregnancy test. A positive pregnancy screen is cause for withdrawal from the protocol.
- g. If the subject continues to meet criteria and the subject reports that they followed appropriate rules and restrictions, the session will proceed.
- h. Review procedures for the experimental session with the subject.
- i. Record the entire session to video and audio. Subjects may review video recordings of their experimental sessions upon request.
- j. The session will last for approximately seven hours or longer.
- k. The therapists will administer the C-SSRS prior to drug administration.
- l. Before drug administration, discuss and review the subject's goals, intentions, and concerns and some of the commonly experienced effects of MDMA.
- m. Instruct the subject not to use caffeine or nicotine two hours before or six hours after the dose of drug.
- n. Subject body temperature will be measured at baseline prior to administration of the

- initial dose and approximately every hour after that. The therapists may make more frequent measurements if body temperature exceeds more than 1°C above baseline.
- o. Subjects will complete the SUD at baseline prior to administration of the initial dose. Subjects will complete the SUD every 60 to 90 minutes, until the session is over, allowing a window of up to 30 minutes to fit into the therapy process where a natural break occurs. If necessary, the therapists can make a greater number of measurements, as their clinical judgment dictates.
 - p. Measure BP, pulse, and BT at baseline prior to drug administration.

During:

- q. At approximately 10:00 in the morning, subjects will receive the initial dose of drug along with a glass of water.
- r. The subject will sit or recline on comfortable furnishings. Eyeshades and a program of music will be provided if the subject wishes to use them. Subjects may speak to the therapists whenever they wish, who will provide guidance and support, as needed.
- s. Measure BP, pulse, and BT once every hour throughout the experimental session. More frequent measures will be taken if clinical signs and symptoms of hypertension are observed. If BP values are sustained at 180 systolic and/or 110 diastolic, the PI will make a decision about whether to conduct additional measurements or to provide treatment. Measurements may be repeated until they have been decreasing for 15 minutes or have stabilized at a level judged by the PI to be safe.
- t. After the first hour, if the subject has not spoken spontaneously, check in with him/her about the nature of the experience. For the rest of the experience, as appropriate, the therapists will support and encourage the subject in emotional processing and resolution of whatever psychological material is emerging.
- u. Approximately two hours after drug administration during the second experimental session, prepare the subject for the blood draw for biomarker analysis. Bring in the phlebotomy technician when the subject is emotionally ready for the blood draw.
- v. Initiate the TASIT. The TASIT administration may be spread out between hours two and three to fit around the therapeutic process.
- w. Record any spontaneously reported reactions during the session.
- x. Provide water and electrolyte containing fluids throughout the session but not to exceed 3 L overall.
- y. Provide food during the latter part of the session.
- z. If it is appropriate to do so, initiate the first question of the C-SSRS at any point in the session if the subject is experiencing significant psychological distress that does not respond readily to processing with the therapists. The C-SSRS is required at least once during the session. It is preferable to administer it towards the end of the session, about six hours after the initial dose.
- aa. End the session if all medical and psychiatric parameters are acceptable and the subject is alert, ambulatory, and emotionally stable.

Post-drug:

- bb. The therapists will depart from the site when they have concluded that the subject is emotionally and medically stable. Therapists shall remain available to subjects during the experimental session and for one week after via 24 hour cellular phone for

- integration, as needed.
- cc. Spontaneously reported reactions, AEs, and concomitant medications will be collected, as described in Section 8.5 and Section 9.0.
 - dd. Assess status of symptoms at baseline specific to the study population.
 - ee. After the experimental sessions, an overnight stay at a hotel located close to the site will be offered to subjects, accompanied by their support partners, if they live further than 30 miles from the site.
 - ff. During the night of the experimental session, subjects will be given the following measures to complete prior to the integrative session on the next day:
 - a. RSES
 - b. IRI
 - c. PSS

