An overnight stay at a hotel located close to the site will be offered to subjects, accompanied by their support partners, if they live further than 30 miles from the site. Subjects will attend a 1-hour follow-up integrative therapy session on the day after the experimental session. Two additional integrative sessions will be conducted within the month following each experimental session, prior to outcome assessments being conducted one month after each experimental session. During integrative therapy sessions subjects will receive support in integrating their experiences and insights from the experimental session. The second experimental session will be scheduled approximately one month after the first experimental session, after outcome assessments have been completed.

All subjects, even those who have a prior diagnosis, will be clinically evaluated by the PI to determine autistic status. In addition, autistic status will be confirmed with the gold-standard diagnostic measure of autism and diagnosis of co-morbid psychological disorders will be conducted according to DSM-IV criteria at screening. Outcome measures will be assessed prior to treatment, during the treatment period, one month after each experimental session, and during the 6-month follow-up according to the Time and Events table. The sponsor will conduct an ongoing review of videos of therapy sessions, entry criteria, vital signs, and reaction data for completed sessions and any AEs. The sponsor will provide ongoing feedback to the co-therapist teams to ensure subject safety.

For all subjects blood samples will be obtained for biomarker analysis at baseline and during the study according to the Time and Events Table. Biomarker analyses including plasma OT, AVP, and CORT will be explored as surrogate endpoints at baseline, two hours after drug administration during the second experimental session, one month after the second experimental session, and at 6-month follow-up. Blood will be collected during the open-label extension Stage 2 two hours after drug administration during both

experimental sessions and one month after both experimental sessions. Biomarkers will be evaluated for predictive and prognostic power.

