4.2 Recruitment and Subject Population

Subjects may be male or female, aged 21 or older, with a confirmed diagnosis of autism and two years of college-level education or comparable vocational training. Verbal and written proficiency in English will be required. Subjects communicating with text-to-speech technology will also be permitted. Therefore, the researchers anticipate that all subjects will have an AS diagnosis or a diagnosis of Autistic Disorder, as defined in the DSM-IV, coupled with strong verbal proficiency. Subjects must meet all protocol inclusion criteria and no exclusion criteria at baseline. Subjects must be in good physical health and without major medical disorders that might affect the safety or tolerability of MDMA. Subjects must be MDMA-naïve. Subjects will be asked to confirm that they will not take MDMA outside of the context of study participation during the study. Subjects will be recruited through printed advertisements, internet advertisements and discussion forums, referrals from other psychiatrists, psychotherapists or physicians, and through word-of-mouth.

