4.2.1 Inclusion Criteria

Individuals eligible to be enrolled into this protocol are subjects who:

1. Be diagnosed with Autism Spectrum Disorder;
2. Have at least moderate to severe Anxiety;
3. Have had at least one unsuccessful attempt at treatment for PTSD either with talk therapy or with drugs, or discontinuing treatment because of inability to tolerate psychotherapy or drug therapy.
4. Are at least 21 years old;
5. Have completed two years of college-level education or comparable vocational training;
6. Must be generally healthy;
7. Must sign a medical release for the investigators to communicate directly with their therapist and doctors;
8. Are willing to refrain from taking any psychiatric medications during the study period;
9. Willing to follow restrictions and guidelines concerning consumption of food, beverages, and nicotine the night before and just prior to each experimental session;

10. Willing to remain overnight at the study site;
11. Agree to have transportation other than driving themselves home or to where they are staying after the integrative session on the day after the MDMA session;
12. Are willing to be contacted via telephone for all necessary telephone contacts;
13. Willing to give blood samples;
14. Must have a negative pregnancy test if able to bear children, and agree to use an effective form of birth control;
15. Must provide a contact in the event of a participant becoming suicidal;
16. Are proficient in speaking and reading English;
17. Agree to have all clinic visit sessions recorded to audio and video
18. Agree not to participate in any other interventional clinical trials during the duration of this study.

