5.4 Removal of Subjects from the Study

Subjects can withdraw consent at any time without prejudice. The therapists can withdraw a subject if, in their clinical judgment, it is in the best interest of the subject or if the subject cannot comply with elements of the protocol that are critical for safety or for the scientific integrity of the study. If the therapists withdraw a subject from the study, the therapists will explain the reason for withdrawing the subject. The reason for early termination will be recorded in the subject's Source Records and CRF.

If a subject develops any exclusion criteria that in the opinion of the Medical Monitor, affects the safety of the subject, including psychiatric diagnosis, pregnancy, or requiring use of excluded medications, the subject will discontinue treatment but remain in the study for follow-up purposes. Whenever possible, the tests and evaluations listed for the follow-up will be carried out. Efforts will be made to obtain information about AE outcomes, if deemed necessary by the PI, Data Safety Monitor, Medical Monitor, and/or sponsor.

Subjects discontinuing treatment before the first experimental session will be replaced until blinded data has been collected from 12 subjects. Subjects who discontinue participation after the first experimental session will not be replaced, and an intent-to-treat analysis will be conducted with all available data. Subjects discontinuing treatment prior to the second experimental session will be asked to complete integrative therapy sessions, outcome assessments prior to discontinuation and complete the six-month follow-up assessment if possible. The blind will not be broken for these subjects until after the six-month follow-up assessments have been completed.

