8.4 Protocol Deviations

All protocol deviations will be included as a categorized listing. Safety and Intent to Treat analyses will include all enrolled subjects with all available data. Subjects with major deviations will be excluded from the per protocol analyses. Major deviations will be defined as anyone who completes through the primary endpoint and anyone who was enrolled but found to not meet inclusion/exclusion criteria during the course of the study. The number of subjects in each protocol deviation category listed below will be summarized by MDMA group, and individual subjects will be listed in the appendix.

Possible protocol deviations include the following seven categories:

- Subject entered study but did not meet criteria
- Subject developed withdrawal criteria but was not withdrawn
- Subject received excluded concomitant treatment
- Protocol procedure not performed per protocol
- Subject received incorrect treatment or incorrect dose
- Protocol procedure performed out of range
- Miscellaneous

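### Protocol 5.2.3 can be read to re-apply the anxiety-severity entry criterion before session 2, and SAP 8.4 to drop a subject who no longer meets it from the per-protocol set; the sections need reconciling

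*Protocol*

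**What the plan says.** Protocol 5.2.3 lists the pre-drug steps for an experimental session. Item c reads "Confirm continuing eligibility by reviewing inclusion/exclusion criteria". Item g reads "If the subject continues to meet criteria and the subject reports that they followed appropriate rules and restrictions, the session will proceed". The opening of the same section says "Procedures for drug-assisted therapy will remain the same across all sessions", so both items apply at the second session (V10) as well as the first (V6).

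Inclusion criterion 2 in Protocol 4.2.1 is "Have at least moderate to severe Anxiety". It names no scale, cut-off or time point.

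Two other sections treat eligibility differently. Protocol 4.2 says "Subjects must meet all protocol inclusion criteria and no exclusion criteria at baseline". Protocol 5.4 ends treatment under this condition: "If a subject develops any exclusion criteria that in the opinion of the Medical Monitor, affects the safety of the subject". Its examples are a psychiatric diagnosis, pregnancy and the need for an excluded medication.

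SAP 8.4 excludes subjects with major deviations from the per-protocol analyses. One limb of its definition of a major deviation is "anyone who was enrolled but found to not meet inclusion/exclusion criteria during the course of the study". The same section keeps all enrolled subjects in the ITT and Safety analyses.

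**The concern.** Most entry criteria are fixed or concern safety. Criterion 2 is different, because it describes the kind of symptom the treatment is meant to reduce and can lapse because treatment works. Staff will have severity data in hand by then: Protocol 4.0 says "The second experimental session will be scheduled approximately one month after the first experimental session, after outcome assessments have been completed", and Table 2 places an LSAS at V9.

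If the session-day check covers criterion 2, two things could follow for a subject who is now below moderate. Session 2 might be withheld. The subject might also be counted as a major deviation and leave the per-protocol set. Both would depend on response after randomization. If MDMA works, both would fall more often on the MDMA arm, and the per-protocol estimate would lose some of its best responders. The trial's stated use is to supply effect sizes for later studies, so an analysis set that depends on the outcome is worth closing off.

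**Working it through.** There is no figure in the plan to reproduce. Protocol 12.1 and SAP 6.0 give no power calculation, effect size or SD. The check is mainly textual.

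**Which criteria apply, and when**

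- Protocol 5.2.3, items c and g: the inclusion/exclusion list, on each session day, with no exemptions. The section states consequences for a positive drug screen and a positive pregnancy test, but none for a lapsed severity criterion.
- Protocol 4.2: the criteria, at baseline.
- Protocol 5.2.2: final confirmation of eligibility at Visit 3. Item d then has therapists ask about changes in health so as to confirm continuing eligibility, and about medication taper.
- Protocol 5.4: eligibility-related stopping is for a newly developed exclusion criterion that affects safety. Loss of an inclusion criterion is not listed.
- Protocol 4.0: each subject has two sessions, and dose escalation at the second is qualified only by safety and tolerability.

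The literal scope of 5.2.3 is therefore wider than that of 4.2 or 5.4, and nothing says which section governs at V10.

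**What SAP 8.4 does with such a subject**

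The limb quoted from SAP 8.4 has two readings: ineligible at entry and discovered later, or no longer meeting a criterion at some later point. The matching deviation category in the same section concerns subjects who entered without meeting criteria, which favours the first reading. The time phrase in the limb allows the second.

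**How many subjects it could touch**

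Allocation is 8 MDMA to 4 placebo. If a share p of MDMA subjects falls below the criterion after session 1 (p is an assumption), the chance that at least one is affected is 1 − (1 − p)^8:

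- p = 10%: 1 − 0.9^8 = 57%; expected 8 × 0.10 = 0.8 subjects
- p = 25%: 1 − 0.75^8 = 90%; expected 2
- p = 50%: 1 − 0.5^8 = 99.6%; expected 4

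**What it could do to a per-protocol estimate (illustration only)**

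Assume the check uses LSAS 55, the lower end of the moderate band in 5.1.2; the documents do not link that band to criterion 2. Assume also a baseline mean of 85, SD 15 and minimum 55; mean changes of −25 (MDMA) and −10 (placebo) at both V9 and V13, with SD 18; and a correlation of 0.7 between the V9 and V13 changes. By simulation, 40% of MDMA and 18% of placebo subjects are below 55 at V9. The V13 difference in mean change is 25 − 10 = 15.0 points with everyone included and 11.8 without those subjects. With a correlation of 0.4 it is 13.2.

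Over baseline means of 75 to 95, MDMA changes of −15 to −35 and correlations of 0.4 to 0.7, the difference shrinks by 8% to 28%. A second set assumes baseline means of 75 to 95, SD 15 and minimum 60; a change SD of √(10² + 8²) = 12.8; a correlation of 100/164 = 0.61; a placebo change of −10 at both visits; and an MDMA change of −25 or −35 at V13, with half the drug effect present at V9. It gives 4% to 8%.

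Both sets leave the V13 score unaffected by a missed session. With SD 18, the standard error of the difference at 8:4 is 18 × √(1/8 + 1/4) = 11.0 points. The 15.0 − 11.8 = 3.2 point shift is thus about 0.29 of a standard error.

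**The case against.** A reader might infer that 5.2.3 is a stopping rule under which any subject who improves fails the check, becomes a major deviation and pulls the trial's main effect estimate toward zero. The documents do not support that.

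- Item g says the session proceeds if criteria are met. It does not say only if, and it states no action for a lapsed severity criterion.
- Improvement alone would not fail criterion 2. The subject would have to fall below moderate, which is undefined. Table 2 has no LSAS on session days, and nothing ties the V9 score to the check.
- Taken together, 4.2, 5.2.2, 5.4 and 4.0 suggest that the session-day check concerns health, medication and safety. An investigator who knows the whole protocol may well never cancel a session because a subject improved.
- The SAP phrase more naturally means ineligible at entry and found out later.
- Exclusion as a major deviation affects only the per-protocol set. SAP 8.10.1 does not assign the primary test to that set.

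All of this stands. What remains is that 5.2.3 exempts nothing, that it differs in scope from 4.2 and 5.4, and that the SAP wording leaves an outcome-dependent exclusion open.

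Two qualifications apply in the other direction. If session 2 were withheld, the subject's V13 score would reflect one session even in an ITT analysis. SAP 8.1 also requires completion of Stage 1 for the per-protocol set, so such a subject might be lost by that route whatever 8.4 says.

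**Conclusion.** The concern holds as an unresolved inconsistency of low severity. Read literally, 5.2.3 re-applies criterion 2 before session 2, while 4.2 and 5.4 point elsewhere. SAP 8.4 can then be read to remove a subject from the per-protocol set because of response. The texts permit this chain but do not compel it.

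The size of any bias cannot be derived from the documents. The illustrative shrinkage of 4% to 28% rests wholly on assumed means, SDs, correlations and a cut-off. It applies only if the literal reading is followed and the affected subjects are excluded. It does not show that the primary or ITT estimate is biased by these amounts. The firmer point is that, with eight MDMA subjects, even a modest lapse rate makes it more likely than not that the question will arise at least once.

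**What to change.** **Protocol.** Reconcile 4.2, 4.2.1, 5.2.3 and 5.4. State in 5.2.3, by number, which inclusion and exclusion criteria the session-day check covers, including whether criterion 2 is among them. That choice is the sponsor's.

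**SAP 8.4.** Replace the limb "anyone who was enrolled but found to not meet inclusion/exclusion criteria during the course of the study" with: anyone enrolled and found, at any time, not to have met the inclusion/exclusion criteria at enrolment. A later change in severity could then not remove a subject from the per-protocol set as a major deviation.

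The other limb of that sentence, as worded, makes a major deviation of everyone who reaches the primary endpoint. That is a separate fault, but it can be corrected in the same edit.

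**Cost.** About one sentence in each document, with no extra data, visits or subjects.
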